### **5.3 Additional Endpoints**

- Urine pregnancy.
- Attempts to quit smoking.
- Residual volume.
- Apo B/Apo A1 ratio.
- Albumin quantity excreted in 24h.

## 5.4 Study Hypotheses And Evaluation Criteria

### 5.4.1 Hypotheses

This study has no formal pre-specified hypotheses associated with the study objectives. Estimates of THS 2.2 effect will be presented and 95% CI will accompany all effect estimates. Two-sided p-values (null hypothesis of no difference between groups) will be presented for baseline comparability and for the THS 2.2 effect on endpoints in the “smokers’ health profile”, on BoExp to HPHCs, and on BoExp to nicotine. The objective of the study is to determine the effect of THS 2.2 compared to CC at Week 52 on the components of the “smokers’ health profile” as defined by PMI (Protocol Table S1), and to provide additional information to the results of the original study (ZRHR-ERS-09-US) for a prolonged exposure period.

### 5.4.2 Evaluation Criteria

The study will target to describe the 95% confidence intervals (CI) of the THS 2.2 effect as compared to CC at Week 52 on the components of the “smokers’ health profile” estimated with a precision of  $\pm 75\%$  of the anticipated THS 2.2 effect at week 52.

## 6 INVESTIGATIONAL PLAN

### 6.1 Study Design

This study is a 26 week extension study of the original study (ZRHR-ERS-09-US), a randomized, controlled, open-label, 2-arm, parallel group study design conducted over a 26 week period. This 6-month extension study will be conducted as a separate study, as a follow-up of the 6-month randomized exposure period of the original study, extending the exposure to a 12-month randomized exposure period from V4-V10 (Day 1 - Week 26, 6 months) to V4-V16 (Day 1 - Week 52, 12 months), using the same sites. Subjects will continue to use the product they were randomized to in the original study (THS 2.2 arm or CC arm).

[figure not shown]
The extension study will be an *ad libitum* smoking study with unrestricted product use for the duration of the study (including during site visits).

The end of the study (EOS) for the individual is defined as the date of the last visit of the subject plus 28 days of Safety Follow-up Period. For subjects lost to follow-up the individual end of study is the discontinuation date. End of Study for whole study is the last subject individual EOS.

Subjects that terminate the study after enrollment and prior to completion of the extension study will undertake early termination procedures.

Figure 1 Study Flowchart

Abbreviations: CC = conventional cigarette(s); THS = Tobacco Heating System

## 6.2 Selection of Study Population

All subjects who have completed the 26 week randomized exposure period (V10) of the original study will be potentially eligible for enrollment into the extension study, depending on whether or not they want to participate and if they meet the entry criteria.

The maximum number of subjects that can be enrolled is pre-defined by the number of subjects completing the 26 week period of the original study. The target population in the original study was approximately 950 female or male, healthy adult smokers. All races/ethnicities were considered eligible, although a quota was applied to subjects of

Caucasian origin (Race is White and Ethnicity is Not Hispanic or Latino), as they should not represent more than 75% of the randomized subjects.

### 6.2.1 Inclusion Criteria

At V10, each subject must meet the following criteria to be eligible to enter in the extension study:

Inclusion Criteria	Screening at V10
1. Subject has completed V10 of the original study (ZRHR-ERS-09-US).	X
2. Subject has signed the ICF at V10 and is able to understand the information provided in the ICF.	X
3. The subject is willing to comply to study procedures and to continue to use the product he/she was allocated to during the original study (THS 2.2 or CC) for an additional 26 weeks.	X

### 6.2.2 Exclusion Criteria

Subjects who meet any of the following exclusion criteria must not be enrolled into the study:

Exclusion Criteria	Screening at V10
1. As per judgment of the Principle Investigators (PIs) or designee(s), the subject cannot participate in the study for any reason (e.g. medical, psychiatric and/or social reason).	X
2. Any medical conditions that in the opinion of the PI(s) or designee(s) would jeopardize the safety of the participant.	X
3. Subject has made a quit attempt* during the original study.	X
4. For women only: Subject is pregnant (does not have a negative pregnancy test at V10) or is breast feeding.	X

5. For women only : Subject does not agree to use an acceptable method of effective contraception**.	X
--	---

\* From using tobacco-containing products (e.g. THS 2.2 and CC). This information will be captured from the original study.

\*\* e.g., Intrauterine device, intrauterine system, established use of oral/injectable/implantable/transdermal hormonal methods, barrier methods of contraception (condoms, occlusive caps) with spermicidal foam/gel/film/suppository, vasectomized partner(s), or true abstinence (periodic abstinence and withdrawal are not effective methods) from V10 until V16. Hysterectomy, tubal ligation, bilateral oophorectomy or post-menopausal status are reasons for not needing to use birth control. Post-menopausal status is defined as women who have not experienced menses for greater than 12 months.

### 6.3 Product Allocation and Blinding

#### 6.3.1 Methods of Assigning Subjects to Product Arms

During the extension study, subjects will remain in the study arm they were randomized to in the original study (THS 2.2 arm or CC arm in a 1:1 ratio).

Randomization was done during the original study at V4 through the interactive voice and web response system (IXRS).

#### 6.3.2 Blinding

This is an open-label study; therefore, the subjects and Investigators will be unblinded to subject’s arm after randomization at V4 during the original study. However, and similar to the original study there will be a limited degree of blinding during the conduct of the extension study, including the data review and data analysis process. In particular, some members of PMI and CRO personnel will be blinded as summarized in Table 4.

**Table 4: Blinding Scheme**

Blinded Study Personnel	Blinded Data	End of Blinding Period
PMI and ████████ study statisticians	Actual values of primary endpoints at V16 	After the SAP finalization or database lock, whichever comes last.
PMI clinical scientist	Actual values of primary endpoints at V16 	After the finalization of PMI blind database review  . Can be actively unblinded when appropriate.

**Table 4: Blinding Scheme**

Blinded Study Personnel	Blinded Data	End of Blinding Period
 To avoid indirect unblinding of the “actual values of primary endpoints” additional data were blinded in the eCRF (e.g., adverse event terms). After SAP finalization or database lock of the original study, whichever comes last, the whole study team will be unblinded to all data collected in the original study, following the process described in the original study protocol.		
 As part of the PMI Quality Control activity, data listings will be reviewed by [REDACTED] and PMI before database lock. Full details will be available in the data review plan.		

Any PMI and [REDACTED] personnel who are not listed in the above table will be unblinded by default.

Unblinded information will not be shared with the blinded study team, until the end of the blinding period (Table 4). PMI will receive blinded and unblinded data for the pre-analysis data review as planned in the data review plan. Blinded data will be accessible by the blinded study personnel in a masked format or presented independent of the subject identifier so to ensure that data cannot be associated within or to a subject. Unblinded data will only be reviewed by the unblinded study team.

### 6.3.3 Adherence to Product Allocation

The number of CC, THS Tobacco Sticks, and other nicotine/tobacco containing product used daily, as reported by the subject and collected in the electronic diary, will be used to monitor product use and evaluate adherence to product allocation.

Adherence to THS 2.2 is defined as at least 70% THS 2.2 use with no more than 5 CC during each single day of the randomized exposure period of the main study. The same criteria will be adopted for the extended 6-month period. The choice of 5 CC per day is based on the definition of the smoking cessation endpoint: abstinence with occasional slips allowed, as reported in European Medical Association (EMA) guidelines [4].

Subjects in the THS 2.2 and CC arm will be considered adherent to the randomized product only if they belong to THS-use and CC-use product categories, respectively (see Section 4.1.2 “Definition of Product Use Pattern Categories”).

For both the THS 2.2 and CC arms, any subjects reporting to having quit using tobacco-containing products (e.g. THS 2.2 and CC) will be considered not adherent to the study product allocated.

Diary adherence is defined as at least 75% diary use during the randomized exposure period and no more than 7 consecutive days of missing diary use during the randomized exposure period.

Product adherence and diary adherence will be used for the definition of the Per Protocol population (see Section 10.3 “Per Protocol”).

## 7 DERIVED AND COMPUTED VARIABLES

Mean change from Baseline (Baseline is defined in Section 4.1.1 “Definition of Special Terms”) is the mean of all individual subjects’ change from Baseline values. Each individual change from Baseline will be calculated by subtracting the individual subject’s Baseline value from the value at the timepoint. The individual subject’s change from Baseline values will be used to calculate the mean change from Baseline.

Mean percent change from Baseline is the mean of all individual subjects’ percent change from Baseline values. Each percent change from Baseline will be calculated by subtracting the individual subject’s Baseline value from the value at the desired timepoint and then dividing this calculated value by the individual subject’s Baseline value and multiplying by 100. When the Baseline value is 0 for at least 1 subject, the percentage change from Baseline will not be calculated and the number of such cases will be tabulated as “Baseline=0” in any descriptive summaries.

Mean percent relative change from Baseline is estimated as:  $100 * (\exp(\log\_mean\_change) - 1)$  where  $\log\_mean\_change$  is computed by averaging differences:  $\log(\text{post baseline value}) - \log(\text{baseline value})$  at the desired timepoint. When the Baseline value is 0 for at least 1 subject, the percent relative change from Baseline will not be calculated and the number of such cases will be tabulated as “Baseline=0” in the descriptive summaries.

Caucasian origin variable will be derived to be considered in the analysis. Caucasian origin is defined as ‘Caucasian’ (Race is White and Ethnicity is Not Hispanic or Latino) or ‘Non-caucasian’ (Race is not White or Ethnicity is Hispanic or Latino).

Reported BMI will be calculated at site from the body weight and height using the following formula:

$$\text{BMI} = \frac{\text{weight in kilograms}}{\text{height in meters}^2} \quad (\text{kg/m}^2)$$

The QT interval corrected using Bazett’s formula (QTcB) will be calculated as follows:

$$QTcB = \frac{QT}{\sqrt[2]{(60/HR)}}$$

The QT interval corrected using Fridericia's formula (QTcF) will be calculated as follows:

$$QTcF = \frac{QT}{\sqrt[3]{(60/HR)}}$$

The geometric coefficient of variation (CV) will be calculated using the following formula:

$$CV = 100\sqrt{e^{\text{var}} - 1}$$

where var = the variance from the log-transformed data.

## 7.1 Clinical Risk Endpoints and Biomarkers of Exposure

### 7.1.1 Clinical Risk Endpoints and Biomarkers of Exposure in Urine

The adjustment for creatinine of the urinary clinical risk endpoints and biomarkers will be calculated as:

Clinical Risk Endpoint or Biomarker (adjusted for creatinine )

$$= \frac{[\text{Clinical Risk Endpoint or Biomarker}]}{[\text{Creatinine}]}$$

where the [ ] indicated concentrations measured from the same 24 hour urine collection.

### 7.1.2 Nicotine Equivalents

The concentration of Neq in 24 hours will be derived according to the formula below. The concentrations reported for free nicotine and its five major metabolites will not be used as analysis variables.

$$\begin{aligned} \text{Neq [mg/L]} &= (\text{free nicotine}[\mu\text{mol/L}] + \text{nicotine-glucuronide} [\mu\text{mol/L}] \\ &+ \text{free cotinine} [\mu\text{mol/L}] + \text{cotinine-glucuronide} [\mu\text{mol/L}] \\ &+ \text{free trans-3'-hydroxycotinine} [\mu\text{mol/L}] \\ &+ \text{trans-3'-hydroxycotinine-glucuronide} [\mu\text{mol/L}]) \\ &* 162.2[\mu\text{g}/\mu\text{mol}] / 1000 [\mu\text{g}/\text{mg}] \end{aligned}$$

N.B. All concentrations must be in  $\mu\text{mol/L}$  before applying the above formula.

The conversion factors will be applied as follows:

Free nicotine	The molecular weight is 162.232 g/mol [5]. Therefore to convert nicotine from ng/mL to nmol/L, the result in ng/mL is multiplied by 6.164.
Nicotine glucuronide	The molecular weight is 338.356 g/mol [6]. Therefore to convert nicotine from ng/mL to nmol/L, the result in ng/mL is multiplied by 2.955.
Cotinine	The molecular weight is 176.218 g/mol [7]. Therefore to transform cotinine from ng/mL to nmol/L, the result in ng/mL will be multiplied by 5.675.
Cotinine-glucuronide	The molecular weight is 352.341 g/mol [8]. Therefore to transform cotinine from ng/mL to nmol/L, the result in ng/mL will be multiplied by 2.838.
Trans-3'hydroxycotinine	The molecular weight is 192.217 g/mol [9]. Therefore to transform trans-3' hydroxycotinine from ng/mL to nmol/L, the result in ng/mL is multiplied by 5.202.
Trans-3'hydroxycotinine-glucuronide	The molecular weight is 368.34 g/mol [10]. Therefore to transform trans-3' hydroxycotinine from ng/mL to nmol/L, the result in ng/mL is multiplied by 2.715.

## 7.2 Questionnaires

### 7.2.1 Fagerström Test for Nicotine Dependence (FTND)

The FTND [12] will be used in its revised version, as updated in 2012 [13]. These questions are to be answered by the subjects themselves. It is conducted at V1 to determine subject's dependence on nicotine and at V10 and V16 to assess any changes in their dependence on nicotine.

Table 5 describes the six questions the questionnaire consists of, and the scores associated with each question.

The FTND total score will be derived by summing the individual item scores if all items are non-missing; if any items are missing the total score will be set to missing. For the FTND total score, descriptive statistics and frequency tables according to the following classification will be provided [13]:

Mild	0 – 3
Moderate	4 – 6
Severe	7 – 10

**Table 5: Scoring for the Fagerström Test for Nicotine Dependence**

	FTND Question	Response	Score
1	How soon after you wake up do you smoke your first cigarette?	Within 5 minutes	3
		6 to 30 minutes	2
		31 to 60 minutes	1
		After 60 minutes	0
2	Do you find it difficult to refrain from smoking in places where it is prohibited?	Yes	1
		No	0
3	Which cigarette would you most hate to give up?	The first one in the morning	1
		Any other	0
4	How many cigarettes per day do you smoke?	10 or less	0
		11 to 20	1
		21 to 30	2
		31 or more	3
5	Do you smoke more frequently during the first hours after waking up than during the rest of the day?	Yes	1
		No	0
6	Do you smoke even if you are so sick that you are in bed most of the day?	Yes	1
		No	0

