- Myeloperoxidase (MPO), apolipoprotein A1 and B (Apo A1 and Apo B), high sensitivity C-reactive protein (hs-CRP), and low density lipoprotein cholesterol (LDL-C), in serum.
 - Fibrinogen and homocysteine in plasma.
 - Albumin in urine (expressed as concentration adjusted to creatinine).
 - Platelet count and hemoglobin glycosylated (HbA1c in whole blood).
 - Blood pressure, weight, and waist circumference.
6. To describe the changes in subjective effects of smoking in smokers who have switched from CC to THS 2.2 as compared to those who have continued to smoke CC.

Endpoint over the duration of the study:

- Product evaluation: subscales from the modified cigarette evaluation questionnaire (MCEQ).

Confidentiality Statement

Data and information contained in this document are considered to constitute trade secrets and confidential commercial information, and the legal protections provided to such trade secrets and confidential information are hereby claimed under the provisions of applicable law. No part of this document may be publicly disclosed without the written consent of Philip Morris Products S.A.

7. To describe the intention to use THS 2.2 in smokers who have switched from CC to THS 2.2.

Endpoint at V16 (Week 52):

- Intention to use associated with THS 2.2: item scores from intent to use questionnaire for THS 2.2 (ITUQ) only for subjects in the THS 2.2 arm.

8. To describe the change in tobacco dependence in smokers switching from CC to THS 2.2 as compared to those continuing to smoke CC.

Endpoints at V16 (Week 52):

- Score from the Fagerström (FTND) questionnaire.
- Time to first cigarette from the FTND questionnaire.

9. To describe the effect of combined product use (dual use) over the study on the components of the “smokers’ health profile”.

Endpoint:

- The levels of the components in the “smokers’ health profile” and the number of CC and THS Tobacco Sticks used daily as reported on the self-reported product use electronic diary.

10. To evaluate the safety profiles associated with THS 2.2 and CC.

Endpoints over the duration of the study:

- Adverse events (AEs), serious adverse events (SAEs) and device events, including THS 2.2 malfunction/misuse.
- Vital signs.
- Electrocardiogram (ECG).
- Clinical chemistry, hematology and urine analysis safety panel.
- Physical examination.
- Concomitant medications.

Confidentiality Statement

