**Table 6: Modified Cigarette Evaluation Questionnaire - Questions and Subscales**

	Question	Subscale
1	Was smoking satisfying?	Smoking Satisfaction
2	Did cigarettes taste good?	Smoking Satisfaction
3	Did you enjoy the sensation in your throat and chest?	Enjoyment of Respiratory Tract Sensations
4	Did smoking calm you down?	Psychological Reward

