## **12.7.3 Exploratory Analysis**

### **12.7.3.1 Questionnaires**

#### **12.7.3.1.1 FTND Questionnaire**

The FTND (Section 7.2.1 "Fagerström Test for Nicotine Dependence (FTND)") score, the number and percent of subjects in each category of the FTND score (Mild/ Moderate/ Severe) and the response to the first item of the FTND ("Within 5 minutes", "6 to 30 minutes", "31 to 60 minutes", "After 60 minutes") will be summarized and listed at V1, V10 and V16 (Listing 15.3.5.1; Tables 15.2.4.13.1 and 15.2.4.13.2).

The change from V1 in the FTND score category and response to the first item of the FTND will be presented in a shift table.

All summaries and shift tables will be performed on the FAS-EX (using the product use pattern category) and PP population.

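### In the FTND tables for objective 8, the cigarette count item falls automatically for THS-use subjects, so a lower dependence class can appear with no change in dependence

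*SAP*

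**What the plan says.** Objective 8 in Protocol 3.2 is "To describe the change in tobacco dependence in smokers switching from CC to THS 2.2 as compared to those continuing to smoke CC". Its endpoints are the FTND score and the time to first cigarette.

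SAP 7.2.1 repeats the questionnaire "at V10 and V16 to assess any changes in their dependence on nicotine", the reference being V1, and says that Table 5 sets out its six questions. In that table:

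- Item 1 (0-3 points): "How soon after you wake up do you smoke your first cigarette"
- Item 3 (0-1 point): "Which cigarette would you most hate to give up"
- Item 4 (0-3 points): "How many cigarettes per day do you smoke", scored 0 for 10 or less, 1 for 11-20, 2 for 21-30 and 3 for 31 or more.
- Items 2, 5 and 6 (0-1 point each) refer to smoking without naming cigarettes, for example "Do you find it difficult to refrain from smoking in places where it is prohibited"

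Neither document describes a THS version of the items or an instruction to count THS sticks.

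SAP 12.7.3.1.1 plans shift tables from V1 and says "All summaries and shift tables will be performed on the FAS-EX (using the product use pattern category) and PP population". Protocol 12.6.2 names the same two sets. SAP Table 1 defines THS-use by a THS share of at least 70% of sticks plus cigarettes over the period, together with a condition on the proportion of days.

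**The concern.** The objective names tobacco dependence, but item 4 counts only one of the two products, and the tables group subjects by the split between those products. A subject who replaces most cigarettes with the same number of THS sticks must score lower on item 4, and the shift table will show that as lower dependence.

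The bias has one direction, in favour of THS 2.2. No planned FTND table compares all randomised subjects by arm. The PP set is analysed as randomised, but its THS 2.2 arm is limited to THS-use subjects, so it has the same problem. At stake is whether the tables can be read as an answer to objective 8.

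**Working it through.** **Check of the scale.** The item maxima in Table 5 sum to 3+1+1+3+1+1 = 10, which matches the top of the severe class (7-10) in SAP 7.2.1. Items 1, 3 and 4 hold 3+1+3 = 7 points.

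**Inputs.** T is the cigarettes per day at V1. At V10 or V16 the total is still T, now as THS+CC. At the THS-use threshold, CC = 0.30 × T. Item 4 is scored with the Table 5 bands.

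| T (units/day) | CC at 30% | Item 4 at V1 | Item 4 later | Change |
|---|---|---|---|---|
| 10 | 3.0 | 0 | 0 | 0 |
| 11-20 | 3.3-6.0 | 1 | 0 | -1 |
| 21-30 | 6.3-9.0 | 2 | 0 | -2 |
| 31-33 | 9.3-9.9 | 3 | 0 | -3 |
| 34-35 | 10.2-10.5 | 3 | 0 or 1, by rounding | -3 or -2 |
| 36-60 | 10.8-18.0 | 3 | 1 | -2 |

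These are the falls at exactly 70% THS. A higher share cannot make them smaller: at 95% THS and T = 40, CC is 0.05 × 40 = 2.0 and the fall is 3. If item 4 counted sticks plus cigarettes, the change would be 0 in every row.

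**Effect on the class** (mild 0-3, moderate 4-6, severe 7-10):

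- A fall of 1 moves totals of 4 or 7 down one class.
- A fall of 2 moves totals of 4-5 or 7-8.
- A fall of 3 moves totals of 4-6 or 7-9.
- Severe to mild needs at least 7 - 3 = 4 points, more than item 4 can lose.

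Example: a subject at 20 cigarettes/day with a V1 total of 4 later uses 14 sticks and 6 cigarettes. Total use is unchanged, item 4 goes from 1 to 0, and the class goes from moderate to mild.

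**Dual-use.** The fall is possible but not forced. At T = 20 with half the units as THS, CC is 10 and item 4 goes from 1 to 0. At T = 12 with 10% THS, CC is 10.8 and item 4 stays at 1.

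**Adherent subjects.** A subject who meets the rule in SAP 6.3.3 of at most 5 cigarettes on any day always scores 0 on item 4.

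**Items 1 and 3.** A THS-use subject may smoke up to 30% of units as cigarettes and can still smoke one within 5 minutes of waking. Only a subject who smokes no cigarettes and answers literally loses these points. That subject scores at most 10 - 7 = 3, which is mild.

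**The case against.** The strongest defence is that little depends on this output. The FTND has no model or test, sits under Exploratory Analysis in the SAP, and its tables are not flagged for topline or ClinicalTrials.gov in SAP 16.4. Item 1 is shown separately, under an endpoint name that already refers to the first cigarette. Nicotine equivalents and plasma nicotine and cotinine are compared by use category in SAP 12.7.2.3. This limits the consequence, but those markers measure exposure, not dependence, and cannot correct the FTND shifts.

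The electronic questionnaire screens and subject instructions are not in the documents, so an adaptation may exist without being described. Usage is also mixed: Protocol 7.3.5.1 separates smoking from using THS 2.2, while Protocol 4.1 calls the whole study a smoking study. That leaves items 2, 5 and 6 open. It does not change item 4, which SAP 7.2.1 presents as one of the questions.

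Three stronger readings are tempting, and the documents do not support them:

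- *The whole score falls by construction.* Only item 4 is tied to the grouping, and only from 11/day upward. THS-use is a share, not a limit on cigarettes: at 40 units/day, 12 cigarettes still qualify and item 4 scores 1.
- *Subjects will move from severe to mild.* Item 4 alone cannot do this. It would also need a fall in items that the grouping does not determine.
- *At V1 cigarettes stood for all tobacco use.* SAP Table 7 asks about e-cigarette use over the last year, so this cannot be assumed.

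An exclusive THS user might also leave item 1 or 3 blank, which makes the total missing under SAP 7.2.1. That is conjecture, and such a subject would add nothing to a shift towards mild.

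**Conclusion.** The concern stands for item 4. With unchanged THS+CC use, a THS-use subject at 11 or more units/day loses 1 to 3 points, enough to move some totals down one dependence class and none down two. A shift of that size in the planned tables cannot be read as a change in tobacco or nicotine dependence.

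This assumes that the items were asked as printed, that self-reported cigarettes per day at the visit agree with the diary share (a time-weighted average over the period under SAP 16.3.2, not use on the day), and that total use is counted as sticks plus cigarettes. The documents give no baseline distribution of consumption or FTND totals, so the number of subjects who would change class is unknown. The point should be corrected because it affects a listed secondary objective and favours one product. It does not touch the primary analysis.

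**What to change.** In SAP 7.2.1 and 12.7.3.1.1:

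1. Keep the planned FTND score and shift tables, labelled as cigarette-worded FTND.
2. Add a supplementary presentation at V10 and V16: (a) the total without item 4 (maximum 10 - 3 = 7, so the three classes do not apply), compared with the same total at V1; (b) the total with item 4 rescored from diary mean daily CC plus THS sticks, noting that the source differs from V1.
3. Add a FAS-AR table by randomised arm. This restores the randomised comparison but does not cure the item wording.
4. State that shifts in THS-use or Dual-use will not be interpreted as change in tobacco or nicotine dependence unless the supplementary results agree.

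The cost is a few extra descriptive tables from data already collected. The supplementary scores are not validated, version (b) treats one stick as one cigarette, and version (a) still contains items 1 and 3. Rewording the questionnaire at V16 is not advised, because it would break comparability with V1 and V10.
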